5.2 Study Endpoints

Primary Safety Endpoint:

Major Adverse Clinical Events (MAE) at 1 month, defined as death, target vessel revascularization (TVR), target limb amputation.

Primary Performance Endpoint:

Primary Patency at 6 month, defined as no evidence of clinically significant stenosis ($\geq 50\%$) within the stent graft or immediately above or below the treated arterial segment based on duplex ultrasound (systolic velocity ratio of >2.5), with no clinically-driven re-intervention within the stented segment.

Secondary Safety Endpoints:

- Major Adverse Events (MAE) through follow-up.
- Major adverse vascular event (MAVE) through follow-up defined as stent thrombosis, target limb amputation, clinically apparent distal embolization, defined as causing end-organ damage (e.g. lower extremity ulceration, tissue necrosis, or gangrene), procedure related arterial rupture, acute limb ischemia or bleeding event requiring transfusion.
- Major Blood Loss defined as transfusion of >2 units packed red blood cells (PRBC) through discharge.
- The combined rate of death of target vessel revascularization (TVR), index limb amputation, and an increase in Rutherford-Becker Classification by 2 classes (comparing pre- to post-procedural assessments) through follow-up.
- Deep Vein Thrombosis (DVT) on ipsilateral limb defined as a symptomatic blood clot (thrombus) in the targeted deep vein (e.g. posterior tibial) through follow-up.
- VCSS and Villalta Scale through follow-up.
- Venous Assessment (Miller Scale) through follow-up.

- Stent fracture identified via X-ray through follow-up. (Optional per standard practice. Not applicable if radiological Safety Committee approval is required e.g. BFS Germany).

Secondary Performance Endpoints:

- Technical Success defined as successful delivery of the investigational devices to the identified area and removal of delivery system.
- Procedural Success defined as successful delivery of the investigational devices to the identified area and removal of delivery system in the absence of in-hospital MAEs.
- Clinical Success defined as Limb ischemia improvement by Rutherford-Becker (improvement in scale by ≥ 1) through follow-up.
- Limb ischemia by Rutherford-Becker Classification through follow-up.
- Primary Patency through follow-up.

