11.0 ENDPOINTS AND STATISTICAL ANALYSIS PLAN

11.1 Endpoints Analyses and Reporting of Results

The study objective is to assess the safety and performance of the PQ Bypass System to access, deliver guidewires and implant stent grafts for a percutaneous fem-pop bypass.

The study is a feasibility study with no formal hypothesis testing and therefore no required sample size. Study results will be presented using descriptive statistics. Results from this study will be used to design additional clinical studies.

All subjects will be followed on an intent-to-treat basis. The device performance will be assessed based on a per-protocol analysis of the primary safety and effectiveness endpoints. An Intent-to-treat analysis, along with other secondary analyses, will also be completed and reported.

Demographic, baseline clinical and disease characteristics, procedural results and primary, secondary and all additional endpoints will be summarized using descriptive statistics.

All statistical analyses will be performed using SAS for Windows version 9.1 or higher.

Primary Safety Endpoint Reporting:

Safety assessment is achieved by recording and measuring Major Complication rates/Serious Adverse Event rates associated with the PQ Bypass procedure. The number and percentage 6-month MAE will be presented using descriptive Statistics. Using the Score approximation, the one-sided upper 95% confidence bound will be calculated and presented.

Primary Performance Endpoint Reporting:

Descriptive statistics of the primary performance endpoint which includes total number of patent PQB grafts, number and percentage of patent PQB grafts, and the one-sided 95% CI of the percentage using the Score approximation will be presented. The lower bound of the one-sided 95% CI will be compared to the performance goal of 70% (80% historical control rate – 10% Delta.)

Secondary Endpoint Analysis:

The secondary endpoint of primary assisted and secondary patency will be summarized using Kaplan-Meier survival analysis. Life tables will be created and a Kaplan-Meier survival curve will be presented.

The secondary endpoints of Procedural Success, Clinical Success and Technical

Success will be summarized by providing point estimates, number of subjects, and 95% confidence bounds calculated using the Score approximation.

Demographic, procedural and safety data:

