Demographic and baseline clinical and disease characteristics will be summarized in tables. For continuous variables the summary will include number, mean, and standard deviation and 95% confidence intervals. Summaries for categorical variables will include the number and percent of subjects in each category.

Imputation for Missing Data

Imputations for missing data in (e.g. withdrawn subjects, loss to follow-up, missing data) will not be performed. Analyses will be performed with all available data only.

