In order to approximate the performance rates for this study, the results from the El Camino Hospital (ECH) Study were used. The PQB procedural approach was evaluated in the ECH Study. This study used a similar technique to the interventional approach utilized in the ECH Study. This study also used a stent graft that is very similar to the stent graft used in the ECH Study, the Gore Viabahn Stent Graft. Primary patency at 6 months was approximately 90% in the ECH Study. A more conservative estimate of 85% performance for the PQ Bypass Systems was utilized along with the aforementioned performance goal for the purpose of sample size estimation. To achieve 80% power using a one-sided alpha of 0.05, the sample size is 50. To adjust for lost to follow-up and to maintain consistency with current literature on the use of stent grafts, 60 subjects will be enrolled in this study ((Table 11-1)).

Table 11-1: Non-Inferiority with PQ Bypass Performance of 85%

PG	NI Margin				
	5%	7.5%	10%	12.5%	15%
80%	103	69	50	38	30
85%	368	174	103	69	50
90%	-	1371	368	174	103
95%	-	-	-	1371	368

The sample size was also elected in order to observe the rate of major adverse events. The median number of patients enrolled in stent graft trials reported in the literature is 59 patients (range 15-144).

Surgical Bypass Studies

Clinical data published on existing surgical bypass studies for treating femoropopliteal disease is more limited quantitatively and qualitatively. Most importantly, few studies involve doppler-ultrasound assessments of arterial velocity as a basis of assessing patency (e.g. peak systolic velocity ratio). However, one particular and recent randomized prospective study of the Gore Viabahn stent graft vs. prosthetic bypass surgery provides very reliable data set on surgical outcomes as illustrated in **Table 11-2**.

The randomized prospective study was designed to compare the effectiveness of treating superficial femoral artery occlusive disease percutaneously with expanded polytetrafluoroethylene (ePTFE)/nitinol self-expanding stent grafts vs surgical femoral-to-above knee (AK) popliteal artery bypass with synthetic graft material.

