A conservative estimate of 85% performance for the PQ Bypass Systems was utilized along with the aforementioned performance goal for the purpose of sample size estimation. To achieve 80% power using a one-sided alpha of 0.05, the maximum sample size required is 103 subjects. As the surgical patency rate is extrapolated to be between 82% and 85% and since no loss to follow-up is expected in the study, a sample size of 100 subjects should be sufficient and enrolled in this study (**Table 11-3**).

Table 11-3: Non-Inferiority with PQ Bypass Performance of 85%

PG	NI Margin				
	5%	7.5%	10%	12.5%	15%
80%	103	69	50	38	30
85%	368	174	103	69	50
90%	-	1371	368	174	103
95%	-	-	-	1371	368

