- **Non-device or procedure related death** – Death NOT related to any procedure (index or subsequent) intended to treat the target vessel or death not related to the Study Device.

Deep Vein Thrombosis (DVT) on Ipsilateral Limb

A blood clot (thrombus) in the targeted deep vein (e.g. posterior tibial). A deep vein thrombosis is symptomatic. A deep vein thrombosis is distinct from the presence of mild fibrin/thrombus with no hemodynamic impact or the intentional I occupancy of the vein by the graft or asymptomatic occlusive thrombus (see **Venous Classification** below)

Device Deficiency

Inadequacy of the Study Device with respect to its identity, quality, durability, reliability, safety or performance. Device deficiencies include malfunctions, use errors, and inadequate labeling.

Device Time

Number of minutes from initial Study Device insertion to final Study Device removal. It does not include time needed to perform adjunctive procedures.

Explant

Removal of the Study Device implant for any reason.

Fluoroscopy Time

Total fluoroscopy time (minutes) used during the index procedure and includes time utilized for adjunctive procedures performed during the index procedure.

Intensive Care Unit Time

See post-procedure ICU time

Life Expectancy > 2 Year

The duration of time the test subject is expected survive post procedure. Subjects must not have a concurrent medical condition that would cause expected survival to be less than 2 years.

Malignant Tumor¹

A tumor that invades surrounding tissues, is usually capable of producing metastases, may recur after attempted removal, and is likely to cause death of the host unless adequately treated.

Major Adverse Event (MAE)

¹ <http://www.medilexicon.com>

Composite endpoint of death, target vessel revascularization (TVR) or any amputation of the index limb. See individual events for detailed definitions.

Major Adverse Vascular Event (MAVE)

Composite endpoint of stent thrombosis, target limb amputation, clinically apparent distal embolization, defined as causing end-organ damage (e.g. lower extremity ulceration, tissue necrosis, or gangrene), procedure related arterial rupture, acute limb ischemia or bleeding event requiring transfusion.

Myocardial Infarction (MI)²

Typical chest pain and either a Q-wave or non Q-wave MI as described below. Myocardial infarction is a component of MAE.

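### Six-month patency is analysed on available data only, with no status set for amputation, explant, death or a missing scan, so failed grafts can leave the denominator of the rate compared with 70%

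*Combined protocol and SAP*

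**What the plan says.** - **Endpoint.** The Protocol Summary and section 5.2 define 6-month primary patency by a duplex criterion, "with no clinically-driven re-intervention within the stented segment". The primary patency entry in section 19.0 gives the duplex criterion alone and leaves out the re-intervention clause.
- **Decision.** Section 11.1 says of the patency proportion: "The lower bound of the one-sided 95% CI will be compared to the performance goal of 70" percent, with the bound from the Score approximation. Section 11.2 writes H0 and HA against the same 70%.
- **Populations.** Section 11.1 makes the per-protocol analysis the main one and adds: "An Intent-to-treat analysis, along with other secondary analyses, will also be completed and reported".
- **Missing data.** Section 11.1 bars imputation for withdrawal, loss to follow-up and missing data, then says: "Analyses will be performed with all available data only". No exception is made for the intent-to-treat analysis, and no sensitivity analysis for missing scans is described. Kaplan-Meier is planned only for primary assisted and secondary patency.
- **The events.** Death and limb amputation are counted in the MAE composite. Section 19.0 defines explant as "Removal of the Study Device implant for any reason". None of these is linked to patency.
- **Other scans.** Arterial duplex is also scheduled at discharge (9.4), at 1 and 3 months and at premature withdrawal (9.5). Whether those scans feed the 6-month result is not stated.

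**The concern.** The numerator needs a 6-month patency reading, and the available-data rule takes anyone without one out of the denominator. Some subjects without a reading will be without it because the graft failed: it occluded and the limb was lost, or it was removed. If they are left out, the proportion is estimated in a group selected partly on the outcome, and the bias runs towards clearing 70%. The intent-to-treat analysis would normally expose this, but it follows the same rule.

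The plan makes no allowance for it. Section 11.2 justifies 100 subjects by expecting no loss to follow-up, although its stent-graft calculation had raised 50 to 60 partly for that reason. The population is Rutherford 3–5, which includes rest pain and digital ulceration, so some deaths or amputations within 6 months are foreseeable.

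**Working it through.** **1. Inputs.** One-sided alpha 0.05, 80% power, true patency 85% ("A more conservative estimate of 85% performance for the PQ Bypass Systems was utilized"), goal 70%, N = 100: sections 11.1 and 11.2. The number of subjects without a usable scan is not in the documents and is an assumption throughout.

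**2. The plan's own figure.** With the null variance for alpha and the alternative variance for power:

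n = [1.645·√(p0·q0) + 0.842·√(p1·q1)]² / (p1 − p0)²

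- p0 = 0.70, p1 = 0.85: (0.754 + 0.301)² / 0.0225 = 49.4, so 50. The plan says: "To achieve 80% power using a one-sided alpha of 0.05, the sample size is 50".
- p0 = 0.75, p1 = 0.85: (0.712 + 0.301)² / 0.01 = 102.6, so 103. The plan says: "the maximum sample size required is 103 subjects".

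Both reproduce, as does every filled cell of Tables 11-1 and 11-3.

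**3. Passing rule.** The one-sided 95% Score lower bound is

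L = [p̂ + z²/2n − z·√(p̂(1−p̂)/n + z²/4n²)] / (1 + z²/n), with z = 1.645.

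For 78/100: (0.780 + 0.0135 − 0.0695) / 1.0271 = 0.705, which passes. For 77/100, L = 0.694, which does not. So 78 of 100 is the smallest passing count.

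**4. Effect of dropping k subjects.**

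| k dropped | Smallest pass | Observed rate | Bound | Bound for the same count over 100 |
|---|---|---|---|---|
| 0 | 78/100 | 78.0% | 70.5% | 70.5% |
| 2 | 77/98 | 78.6% | 71.0% | 69.4% |
| 5 | 74/95 | 77.9% | 70.2% | 66.2% |
| 10 | 71/90 | 78.9% | 71.0% | 63.1% |

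The required observed rate hardly moves. The number of patent grafts needed among 100 treated falls from 78 to 74 and 71.

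An example away from the threshold: 75 patent, 15 observed failures, 10 unscanned. Available data give 75/90 = 83.3% with bound 75.9%, which passes. Counting the 10 as failures gives 75/100 with bound 67.3%, which does not.

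**5. Chance of clearing 70% when it should not be cleared.** Let true patency, with these events counted as failures, be exactly 70%. Let a share f of the 100 be failures that drop out. The number dropped is Binomial(100, f). Those remaining are patent with probability 0.70/(1 − f). Sum the exact probability of reaching the passing count for each n.

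| f (assumed) | Patency among those scanned | P(bound > 70%) |
|---|---|---|
| 0 | 70.0% | 0.048 |
| 2% | 71.4% | 0.084 |
| 5% | 73.7% | 0.185 |
| 10% | 77.8% | 0.497 |

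Discreteness does not explain the rise: with true patency of 70% among those scanned, the exact error is 0.048 at n = 100, 0.056 at n = 95 and 0.039 at n = 90.

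**6. Missingness unrelated to patency.** At 85% true patency, dropping 0%, 5% or 10% at random gives pass probabilities of 0.978, 0.971 and 0.964: a small loss of precision and no bias. Counting those subjects as failures gives 0.798 at 5% and 0.415 at 10%.

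**The case against.** A reader might infer that the plan rules amputation, explant and death to be non-failures. It does not; it is silent. An explant can be read as a clinically-driven re-intervention within the stented segment under section 5.2, though not under section 19.0. An occlusion before an amputation or death may already be on a scheduled or withdrawal duplex, and the available-data wording does not forbid using it. A distal amputation may leave the graft scannable. All this stands. It moves the defect from a wrong rule to a missing one, combined with a missing-data rule that by default discards the subject.

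A reader might also infer that the bar is lowered. The goal stays at 70% and the required observed rate at about 78–79%. What changes is who is counted.

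Two further objections have force. A missed scan, or a death with a patent graft, biases the rate only if it is related to patency; classing such a death as patency failure is an estimand choice. And a comfortable result would survive: 81/90 (90%, the interim rate in section 2.4) or 81/95 (85.3%) still passes as 81/100.

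Finally, section 11.1 calls this a feasibility study without formal testing, and deaths and amputations are reported openly as safety endpoints. But the same section compares the bound with 70% and section 11.2 states non-inferiority hypotheses, so the comparison will be read as pass or fail. Safety tables do not correct the patency rate.

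**Conclusion.** The point holds as a gap in the endpoint definition that the available-data rule turns into a possible upward bias, in both the per-protocol and intent-to-treat results. With 5 or 10 of 100 dropped, 74 or 71 patent grafts suffice instead of 78. If 2%, 5% or 10% of subjects are failures that drop out, the chance of clearing 70% at a true 70% is 0.084, 0.185 or 0.497 instead of 0.048. These shares are assumed; the plan itself expects no loss. If nobody is unscanned, or missingness is unrelated to patency, this bias is absent.

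The documents do not support the stronger conclusion that every unscanned subject should be a failure in the intent-to-treat analysis. Under random missingness that rule would itself mislead, as step 6 shows. It belongs in a sensitivity bound. The plan should be changed, but this is not a fatal defect.

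**What to change.** In section 11.1, for 6-month primary patency:

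1. State the denominator. Count as loss of primary patency, carried forward, any of the following recorded before the 6-month scan: patency loss on duplex (including the withdrawal scan), clinically-driven re-intervention, graft explant, or major amputation of the index limb. Define major amputation in section 19.0, because the MAE entry there covers any index-limb amputation.
2. Reconcile the primary patency entry in section 19.0 with section 5.2 and the Protocol Summary.
3. For other subjects without a readable 6-month core-lab scan, including deaths, keep the available-data result. Add a worst-case bound and a tipping-point table showing how many of them must be patent for the lower bound to stay above 70%. In the 75/90 example the answer is 3 of 10, since 78/100 is needed. Label both as sensitivity analyses, not as the intent-to-treat rule.

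The cost is a few sentences and one table, with no new data. The reported rate may be lower. With 10 of 100 unscanned, the worst-case figure is below the available-data one by a tenth of the observed rate: 78.9% against 71.0%, about 8 points, at the smallest passing count. Section 2.4 shows that 6-month results for 30 subjects have been seen, so the rule should be dated and fixed before the final 6-month analysis is run.

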11.2 Sample Size Justification

The sample size chosen for this study has been updated from 60 to 100 patients. The sample size was chosen to demonstrate statistically non-inferiority of the PQ Bypass Systems performance as compared to results previously reported in similar studies:

- for intravascular stent grafts (e.g. Gore Viabahn) – n=60
- for prosthetic surgical bypass - n=100

A larger sample size is required as prosthetic surgical bypass outcomes are superior to those of intravascular stent grafts.

Stent Graft Studies

Clinical data published on existing stent graft techniques for treating femoropopliteal disease have reported 6-month primary patency rates of approximately 80%.^{37,40-42,45,60,61} This average success rate has been used as the historical control for the current study. The standard error reported in the cited studies range from 3% to 12%; the lower limit of one-sided 95% confidence intervals (CI) is approximately 68%.

In order to establish a sample size, a margin of non-inferiority, delta, was set at 10% for the current study to demonstrate non-inferiority of the PQ Bypass Systems to the historical control in terms of patency. This delta reflects the diversity of the lesions to be enrolled in this study and the range of reported performance using similar technology; 6-month primary patency in the studies cited above ranges from 27% to 92%, average lesion lengths range from 9-25cm and the percent occlusions included ranges from 50% to 100%. Due to this wide variety of lesions reported in the literature and the potential diversity of patients and lesion lengths that will be enrolled in this study, a 10% delta is adequate to accurately reflect non- inferiority. This delta sets up a comparison between the lower 95% CI of the PQ Bypass Systems performance to the lower 95% CI reported for the competitive products (~70%).

As such using as historical control rate of 80% and a non-inferiority margin of 10%,

the null and alternative hypotheses of the primary performance endpoint can be written as:

$$H_0: \pi_{PQB_performance} \leq \pi_{PG_performance}$$

$$H_A: \pi_{PQB_performance} > \pi_{PG_performance}$$

where,

$$\pi_{PG_performance} = 80\% \text{ historical control rate} - 10\% \text{ Delta}$$

$$\pi_{PQB_performance} = \text{PQB Systems success rate}$$

The hypotheses for the primary performance endpoint can be rewritten as:

$$H_0: \pi_{PQB_performance} \leq 70\%$$

$$H_A: \pi_{PQB_performance} > 70\%$$

In order to approximate the performance rates for this study, the results from the El Camino Hospital (ECH) Study were used. The PQB procedural approach was evaluated in the ECH Study. This study used a similar technique to the interventional approach utilized in the ECH Study. This study also used a stent graft that is very similar to the stent graft used in the ECH Study, the Gore Viabahn Stent Graft. Primary patency at 6 months was approximately 90% in the ECH Study. A more conservative estimate of 85% performance for the PQ Bypass Systems was utilized along with the aforementioned performance goal for the purpose of sample size estimation. To achieve 80% power using a one-sided alpha of 0.05, the sample size is 50. To adjust for lost to follow-up and to maintain consistency with current literature on the use of stent grafts, 60 subjects will be enrolled in this study ((Table 11-1)).

Table 11-1: Non-Inferiority with PQ Bypass Performance of 85%

PG	NI Margin				
	5%	7.5%	10%	12.5%	15%
80%	103	69	50	38	30
85%	368	174	103	69	50
90%	-	1371	368	174	103
95%	-	-	-	1371	368

The sample size was also elected in order to observe the rate of major adverse events. The median number of patients enrolled in stent graft trials reported in the literature is 59 patients (range 15-144).

Surgical Bypass Studies

Clinical data published on existing surgical bypass studies for treating femoropopliteal disease is more limited quantitatively and qualitatively. Most importantly, few studies involve doppler-ultrasound assessments of arterial velocity as a basis of assessing patency (e.g. peak systolic velocity ratio). However, one particular and recent randomized prospective study of the Gore Viabahn stent graft vs. prosthetic bypass surgery provides very reliable data set on surgical outcomes as illustrated in **Table 11-2**.

The randomized prospective study was designed to compare the effectiveness of treating superficial femoral artery occlusive disease percutaneously with expanded polytetrafluoroethylene (ePTFE)/nitinol self-expanding stent grafts vs surgical femoral-to-above knee (AK) popliteal artery bypass with synthetic graft material.

Methods: From March 2004 to May 2005, 100 limbs in 86 patients with femoropopliteal arterial occlusive disease were identified. Patients had symptoms ranging from claudication to rest pain, with or without tissue loss, and were prospectively randomized for treatment into one of two groups. The limbs were treated percutaneously with angioplasty and one or more self-expanding stent grafts (n=50) or surgically with femoral-to-AK popliteal artery bypass using synthetic Dacron or ePTFE grafts (n=50).

The mean and SD total length of artery stented was 25.6 and 15 cm. Follow-up evaluation with ankle-brachial indices and color flow duplex sonography imaging were performed at 3, 6, 9, and 12 months after treatment.

Patients were monitored for a median of 18 months. No statistical difference was found in the primary patency (P=895) or secondary patency (P=.861) between the two treatment groups. Primary patency at 3, 6, 9, and 12 months of follow-up was 84%, 82%, 75.6%, and 73.5% for the stent graft group and 90%, 81.8%, 79.7%, and 74.2% for the femoral-popliteal surgical group. Thirteen patients in the stent graft group had 14 re-interventions, and 12 re-interventions occurred in the surgical group. This resulted in secondary patency rates of 83.9% for the stent graft group and 83.7% for the surgical group at the 12-month follow-up (**Table 11-2**).

Based on review of the limited literature and the recent long lesion stent graft vs prosthetic surgery randomized study 6-month surgical bypass primary patency rate of 82-85% can be extrapolated.

Table 11-2 Randomized Comparison of Viabahn Stent Graft vs. Prosthetic Surgery

Table IV. Primary patency in femoral-popliteal bypass group and stent graft group

Time post-treatment (months)	N at risk at start of interval	N events during interval*	N censored during interval*	% Free from loss of patency	95% CI
Operative (day 0-30)					
Fem-pop bypass	50	2 (2)	0 (0)	0.960	(0.849, 0.990)
Stent graft	50	2 (2)	0 (0)	0.960	(0.849, 0.990)
3 months (day 31-136)					
Fem-pop bypass	48	3 (5)	1 (1)	0.900	(0.776, 0.957)
Stent graft	48	6 (8)	1 (1)	0.840	(0.705, 0.917)
6 months (day 137-227)					
Fem-pop bypass	44	4 (9)	2 (3)	0.818	(0.680, 0.901)
Stent graft	41	1 (9)	1 (2)	0.820	(0.682, 0.902)
9 months (day 228-319)					
Fem-pop bypass	38	1 (10)	8 (11)	0.797	(0.655, 0.885)
Stent graft	39	3 (12)	1 (3)	0.756	(0.611, 0.854)
12 months (day 320-456)					
Fem-pop bypass	29	2 (12)	8 (19)	0.742	(0.587, 0.846)
Stent graft	35	1 (13)	7 (10)	0.735	(0.587, 0.837)

CI, Confidence interval.

Log-rank $P = .895$.

*Number in parenthesis represents cumulative events or censored observations through end of interval.

Table V. Secondary patency in femoropopliteal bypass group and stent graft group

Time post-treatment (months)	N at risk at start of interval	N events during interval*	N censored during interval*	% Free from loss of patency	95% CI
Operative (day 0-30)					
Fem-pop bypass	50	2 (2)	0 (0)	0.960	(0.849, 0.990)
Stent graft	50	0 (0)	0 (0)	1.000	(1.000, 1.000)
3 months (day 31-136)					
Fem-pop bypass	48	2 (4)	1 (1)	0.920	(0.801, 0.969)
Stent graft	50	6 (6)	1 (1)	0.880	(0.752, 0.944)
6 months (day 137-227)					
Fem-pop bypass	45	3 (7)	2 (3)	0.859	(0.726, 0.930)
Stent graft	43	1 (7)	1 (2)	0.860	(0.728, 0.930)
9 months (day 228-319)					
Fem-pop bypass	40	1 (8)	8 (11)	0.837	(0.701, 0.915)
Stent graft	41	1 (8)	1 (3)	0.839	(0.703, 0.916)
12 months (day 320-456)					
Fem-pop bypass	31	0 (8)	11 (22)	0.837	(0.701, 0.915)
Stent graft	39	0 (8)	9 (12)	0.839	(0.703, 0.916)

CI, Confidence interval.

Log-rank P value = .861.

*Number in parenthesis represents cumulative events or censored observations through end of interval.

Kedora et al J Vasc Surg 2007;45:10-16

McQuade et al J Vasc Surg. 2009 Jan;49(1):109-15

In order to establish a sample size, a margin of non-inferiority, delta, was set at 10% for the current study to demonstrate non-inferiority of the PQ Bypass Systems to the historical control in terms of patency. This delta reflects the limited quantitative and qualitative availability of fem-pop bypass studies in the literature. Therefore, a 10% delta is adequate to accurately reflect non-inferiority. This delta sets up a comparison between the lower 95% CI of the PQ Bypass Systems performance to the lower 95% CI reported for the competitive products (~70%).

As such using as historical control rate of 80-85% and a non-inferiority margin of 10%, the null and alternative hypotheses of the primary performance endpoint can be written as:

$$H_0: \pi_{PQB_performance} \leq \pi_{PG_performance}$$

$$H_A: \pi_{PQB_performance} > \pi_{PG_performance}$$

where,

$$\pi_{PG_performance} = 85\% \text{ historical control rate} - 10\% \text{ Delta}$$

$$\pi_{PQB_performance} = \text{PQB Systems success rate}$$

The hypotheses for the primary performance endpoint can be rewritten as:

$$H_0: \pi_{PQB_performance} \leq 70\%$$

$$H_A: \pi_{PQB_performance} > 70\%$$

A conservative estimate of 85% performance for the PQ Bypass Systems was utilized along with the aforementioned performance goal for the purpose of sample size estimation. To achieve 80% power using a one-sided alpha of 0.05, the maximum sample size required is 103 subjects. As the surgical patency rate is extrapolated to be between 82% and 85% and since no loss to follow-up is expected in the study, a sample size of 100 subjects should be sufficient and enrolled in this study (**Table 11-3**).

Table 11-3: Non-Inferiority with PQ Bypass Performance of 85%

PG	NI Margin				
	5%	7.5%	10%	12.5%	15%
80%	103	69	50	38	30
85%	368	174	103	69	50
90%	-	1371	368	174	103
95%	-	-	-	1371	368

